4.1 Study Design and Duration

This study is designed to evaluate the efficacy and safety of apixaban compared to warfarin (INR target range 2.0 - 3.0), a drug approved and widely employed for the prevention of stroke and systemic embolism in subjects with nonvalvular atrial fibrillation with additional risk factor(s) for stroke. The primary endpoint, a composite of stroke (ischemic, hemorrhagic, or of unspecified type) and systemic embolism will be tested using a noninferiority approach. The trial will be event driven thus the number of subjects required and length of treatment are best estimates based on event rates in similar trials. The expected duration of the study, from first subject, first visit through the last follow-up phone contact for the last subject, is approximately 60 months, but the final duration per subject will be determined by the time required to accrue 433 primary efficacy events. All subjects will be followed from randomization until the study end date.

Eligible subjects will be randomized in a 1:1 ratio to either apixaban or warfarin. Each arm will contain ~7.843 subjects (for a total of ~15.686 randomized subjects). Subjects with AF and at least one additional risk factor for stroke will be evaluated for study eligibility. Emphasis will be placed on recruiting both warfarin naïve and warfarin experienced subjects into the trial. The study will be double-blind, double-dummy, with titration based on central monitoring of INR measurements utilizing encrypted point of care (POC) devices, centralized dosing recommendations, and sham apixaban titration. Subjects will receive active apixaban tablets and placebo warfarin tablets or placebo apixaban tablets and active warfarin tablets.

INR testing frequency will occur at least every month during the treatment period, more frequently during titration and if clinically indicated. Each subject will return to have a blood sample drawn and processed in a POC device. The device will deliver an encrypted result to the Investigator who will telephone or electronically transmit the result. This facility will process the information in a blinded manner and return either a true INR value (in the case of a subject receiving warfarin) or a sham INR value (in the case of a subject receiving apixaban), along with a dosage recommendation. The final dosing decision will rest with the Investigator.

At the INR visits, only INR monitoring with POC device, assessment of outcomes, and assessment of study medication compliance will be performed. In addition, at the quarterly visits during the treatment period (Months 3, 6, 9, 15, 18, 21, 27, 30, 33, 39, 42, 45, 51, 54, 57) assessment of changes in concomitant medication, vital signs and laboratory assessments will be performed and at the yearly visits during the treatment period (Months 12, 24, 36, and 48) physical measurements and a 12 lead ECG will be obtained, and electrocardiograms will be performed. All subjects will be followed for the development of stroke (hemorrhagic, ischemic or unspecified), systemic embolism, myocardial infarction, death, bleeding, hospitalization or treatment discontinuation until the end of the study. Follow-up of subjects who discontinued study drug prior to the attainment of 433 primary events in the study should occur quarterly by a telephone call: the final follow-up visit should be in-person, if at all possible, and should be performed within approximately 30 days after the attainment of 433 primary efficacy events in the study.

SAEs (that occurred within 30 days after the last study dose of double-blind study drug) and study outcomes will be documented at all follow-up contacts.

There are three study periods expected to last up to of 60 months in duration:

(1) a screening period of up to 14 days, (2) a treatment period lasting until the earlier of a subject's treatment

[name]

12

discontinuation and the attainment of 433 primary efficacy events and (3) a follow-up period lasting until the latter of 30 days after treatment discontinuation or the attainment of 433 primary efficacy events.

Expected duration of the study, from first subject first visit through last subject, last visit is approximately 60 months.

4.1.1 Executive Committee

An academic Executive Committee (EC) participated in the development of the protocol and will provide ongoing scientific and operational oversight to the study. The Executive Committee will provide suggestions for potential investigators and National Coordinators, will monitor progress of study enrollment, make recommendations to the sponsor based on the DMC recommendations and oversee the presentation and publication of the trial results. The Executive Committee will include clinical experts representing the specialties involved in management of subjects with atrial fibrillation (cardiology, neurology, electrophysiology, coagulation and thrombosis, or hypertension) and experienced in large clinical trial methodologies.

4.1.2 Clinical Events Committee

The Clinical Events Committee (CEC), composed of experts in the relevant fields, will review in a blinded manner, all reported study outcomes to provide consistency and validity in the assessment of outcomes. Their decisions will be based on blind clinical data and they will consider the impressions of the Investigator. Their decisions will be used for the final statistical analyses.

4.1.3 Data Monitoring Committee

This study will be conducted under the auspices on an independent Data Monitoring Committee (DMC), whose membership and activities are described in the DMC charter. The DMC will include at least 2 cardiologists, a neurologist, as well as a statistician. This committee will review accumulating data on a regular basis, and may request to review partially unblinded (treatment x vs. treatment y) or unblinded accumulating data. The DMC will make recommendations to the Executive Committee and Sponsor regarding the continuing safety of subjects currently enrolled and yet to be enrolled in the trial. At all times during the course of the study, the DMC may request access to unblinded data if needed. The DMC may recommend early termination of the trial, for safety reasons.

4.2 Study Population

4.2.1 Inclusion Criteria

For entry into the study, the following criteria **MUST** be met.

- Age \geq 18 years
- In atrial fibrillation or atrial flutter not due to a reversible cause and documented by ECG (electrocardiogram) at the time of enrollment.

Or

If not in atrial fibrillation/flutter at the time of enrollment, must have atrial fibrillation/flutter documented on two separate occasions, not due to a reversible cause at least 2 weeks apart in the 12 months prior to enrollment. Atrial fibrillation/flutter may be documented by ECG, or as an episode lasting at least one minute on a rhythm strip, Holter recording, or intracardiac electrogram (from an implanted pacemaker or defibrillator).

- One or more of the following risk factor(s) for stroke:
 - 1) Age 75 years or older
 - 2) Prior stroke, transient ischemic attack or systemic embolus
 - 3) Either symptomatic congestive heart failure within 3 months or left ventricular dysfunction with an LV ejection fraction (LVEF) \leq 40% by echocardiography, radionuclide study or contrast angiography
 - 4) Diabetes mellitus
 - 5) Hypertension requiring pharmacological treatment
- Women of childbearing potential (WOCBP) must be using an adequate method of contraception to avoid pregnancy throughout the treatment period of the study or for 2 weeks after the last dose of study medication,

[name]

13

whichever is longer, in such a manner that the risk of pregnancy is minimized.

- All subjects must provide signed written informed consent

4.2.2 Exclusion Criteria

- Atrial fibrillation or flutter due to reversible causes (e.g. thyrotoxicosis, pericarditis)
- Moderate or severe mitral stenosis
- Conditions other than atrial fibrillation that require chronic anticoagulation (e.g. prosthetic mechanical heart valve)
- Recent ischemic stroke (within 7 days)
- Increased bleeding risk that is believed to be a contraindication to oral anticoagulation (e.g. previous intracranial hemorrhage)
- Planned major surgery
- Planned atrial fibrillation or flutter ablation procedure
- Persistent, uncontrolled hypertension (systolic BP > 180 mm Hg, or diastolic BP > 100 mm Hg)
- Active infective endocarditis
- Severe comorbid condition with life expectancy of ≤ 1 year
- Use of an unapproved, investigational drug or device within the past 30 days
- A need for aspirin at dose of > 165 mg a day or for both aspirin and clopidogrel
- Severe renal insufficiency (serum creatinine > 2.5 mg/dL or a calculated creatinine clearance < 25 mL/min)
- Subjects with active liver disease or persistent elevation of liver enzymes/bilirubin:
ALT or AST ≥ 2 times the ULN, TBL ≥ 1.5 times the ULN and ALP ≥ 2 times the ULN
- Active alcohol or drug abuse, or psychosocial reasons that make study participation impractical

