4.2.3 Discontinuation of Subjects from Treatment

Subjects should discontinue study treatment for any of the following reasons:

- Withdrawal of informed consent (subject's decision to withdraw for any reason)
- Any clinical AE, laboratory abnormality or intercurrent illness which, in the opinion of the Investigator, indicates that continued participation in the study is not in the best interest of the subject
- If ALT ≥ 5 x ULN on any two consecutive occasions
- Total bilirubin ≥ 2.0 x ULN on any two consecutive occasions
- Pregnancy
- Termination of the study by BMS

UNIT 5 : Treatments

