6.1.2.2 All Monthly Visits and INR Visits

INR monitoring will begin on the 4th day following initiation of drug administration and will be performed twice a week for two weeks, once a week for two weeks (i.e. Day 4, Week 1, Day 10, Week 2, Week 3, Week 4), and monthly thereafter once a stable INR is obtained, unless the subject is no longer taking IP. INR measurements are to be reinstated if a subject recommences IP as above. Each subject will return to have a blood sample drawn and processed using the POC device. The device will deliver an encrypted result to the Investigator who will telephone or electronically transmit the result along with the subject's identification number, date and time, to a central response facility. This facility will process the information in a blinded manner and return either a true INR (in the case of a subject receiving warfarin) or a sham INR value (in the case of a subject receiving apixaban), along with a dosage recommendation. The final dosing decision will rest with the Investigator. The POC device may be used prior to randomization to determine if the INR value is < 2 .

At the INR visits the Investigator will:

- Perform POC testing for INR
- Obtain laboratory tests for assessment of LFT and CK (at Months 1 and 2 visits only)
- Obtain urine pregnancy test (at all monthly visits)
- Assess for outcomes (death, stroke, systemic embolism, myocardial infarction, bleeding)
- Assess changes in concomitant medication use (at Month 1 visit only)
- Assess for AEs
- Collect Study Medication
- Assess Study Medication use

[name]

19

- Dispense Study Medication

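### The liver exclusion joins its thresholds with 'and', so as written it admits an isolated ALT of 5 × ULN or bilirubin of 2.0 × ULN, levels at which treatment is to stop if they are sustained

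*Protocol*

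**What the plan says.** Protocol section 4.2.2 introduces the liver exclusion with "Subjects with active liver disease or persistent elevation of liver enzymes/bilirubin" and, after a colon, gives the limits in one line: "ALT or AST ≥ 2 times the ULN, TBL ≥ 1.5 times the ULN and ALP ≥ 2 times the ULN". Among the thresholds the only 'or' stands between ALT and AST. The three groups are joined by a comma and then 'and'.

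Two other exclusions in the same list state their alternatives openly. The renal one reads "serum creatinine > 2.5 mg/dL or a calculated creatinine clearance < 25 mL/min" and the blood-pressure one "systolic BP > 180 mm Hg, or diastolic BP > 100 mm Hg".

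Section 4.2.3 opens with "Subjects should discontinue study treatment for any of the following reasons", so one listed reason is enough. Two of the reasons are "If ALT ≥ 5 x ULN on any two consecutive occasions" and "Total bilirubin ≥ 2.0 x ULN on any two consecutive occasions".

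Nowhere else does the protocol say whether the liver limits for entry apply jointly or singly.

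**The concern.** An eligibility threshold is applied at the site as it is written. This line uses 'or' for ALT and AST and 'and' for the rest, in a list that elsewhere writes 'or' when it means alternatives. A site has textual grounds for requiring all three elevations before excluding a subject, and another site may exclude on any one of them.

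Under the literal rule a subject could start a study anticoagulant at a liver test level that section 4.2.3 treats as sufficient reason to stop once it is confirmed. Liver function is relevant to the test drug: section 1.4 puts nonrenal elimination of apixaban at about 75% and names CYP3A4 and SULT1A1 as the main metabolic routes. The stakes are subject safety and uniform eligibility, not the validity of the comparison.

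**Working it through.** No figure in the plan depends on this line, so there is nothing to reproduce. The check is one of logic.

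**Inputs, all in multiples of ULN**
- Entry limits (section 4.2.2): ALT or AST 2, TBL 1.5, ALP 2.
- Stopping limits (section 4.2.3): ALT 5 or total bilirubin 2.0, each on two consecutive occasions.

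**Rules**
- A = (ALT ≥ 2 or AST ≥ 2); B = (TBL ≥ 1.5); C = (ALP ≥ 2).
- Literal exclusion: A and B and C.
- Any-one exclusion: A or B or C.
- At a stopping level: ALT ≥ 5 or TBL ≥ 2.0. The stopping rule is met when the value is repeated.

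The entry rule also requires the elevation to be persistent. The cases below assume that it is, so that only the joining word decides the result.

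| Case | A | B | C | Literal rule | Any-one rule | At a stopping level |
|---|---|---|---|---|---|---|
| ALT 5, AST 1, TBL 1, ALP 1 | yes | no | no | not excluded | excluded | yes (ALT) |
| ALT 1, AST 1, TBL 2.0, ALP 1 | no | yes | no | not excluded | excluded | yes (TBL) |
| ALT 5, TBL 2.0, ALP 1.9 | yes | yes | no | not excluded | excluded | yes (both) |

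In the third case ALP alone, at 1.9 against a limit of 2, defeats the exclusion.

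**How far the two readings differ.** Each of A, B and C is either met or not, giving 2 × 2 × 2 = 8 patterns. The literal rule excludes 1 (all three met). The any-one rule excludes 8 − 1 = 7 (all except none met). They disagree on 7 − 1 = 6 of 8. This counts logical patterns, which are not equally likely among patients, and it is not a rate of subjects.

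**Do the sections agree after correction?** Under the any-one rule, ALT ≥ 5 implies ALT ≥ 2, and TBL ≥ 2.0 implies TBL ≥ 1.5. Both entry limits lie below the matching stopping limits (2 < 5 and 1.5 < 2.0), so no one with persistent values at a stopping level passes the entry thresholds.

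**When the stopping rule could first act.** Section 6.1.2.2 schedules early liver tests at the INR visits: "Obtain laboratory tests for assessment of LFT and CK (at Months 1 and 2 visits only". If the screening value counts as one of the two consecutive occasions, the earliest scheduled trigger is Month 1. If only on-treatment values count, it is Month 2. Section 4.2.3 does not say which applies.

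**The case against.** The strongest reply is that the line is a list of definitions, one cut-off per test, and that 'and' merely closes the list. The slash between enzymes and bilirubin in the lead-in points the same way. Read so, an isolated elevation is excluded and nothing conflicts with section 4.2.3. This is probably what was intended. It does not settle the matter, because the same line and the same list use 'or' for alternatives and no other text resolves the doubt.

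Second, other provisions limit the harm. Active liver disease is a separate ground for exclusion that needs no threshold. Section 4.2.3 also lets the investigator stop treatment for any laboratory abnormality judged to be against the subject's interest, without waiting for a second value. Beyond Months 1 and 2, section 6.2.2 places ALT, AST, ALP and bilirubin in the central laboratory panel at quarterly and annual visits. All of this stands as mitigation, but it either relies on individual judgement or acts only after dosing has begun. It does not repair the entry rule.

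Third, entry and stopping rules serve different purposes and need not match. That is true, and the limits need not be equal. It is still hard to justify an entry rule that admits a level which, once repeated, is by itself a reason to stop.

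Finally, the pattern count says nothing about how many patients are involved, and eligibility is decided before randomization in the same way for both arms, so no bias in the comparison is shown. Both points are accepted, and they keep the weight of the finding low.

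**Conclusion.** The concern holds. As written, the liver thresholds exclude only subjects with all three groups raised. An isolated ALT of 5 × ULN or bilirubin of 2.0 × ULN passes them, although section 4.2.3 says treatment should stop at either level when it is sustained on two consecutive occasions.

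The conclusion rests on the literal reading of 'and'. On the likely intended reading the sections agree, so this is a defect of wording in an operative safety criterion and not an error in the limits. The number of subjects affected cannot be derived from the protocol, and no rate is assumed. Sample size, event count, power and alpha are unaffected. The point is minor, but it should be corrected because eligibility turns on it.

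**What to change.** Reword the liver item in section 4.2.2 so that any single limit excludes, for example: 'active liver disease, or persistent elevation of any one of the following: ALT or AST ≥ 2 × ULN; or TBL ≥ 1.5 × ULN; or ALP ≥ 2 × ULN'. Keep all threshold values, and leave section 4.2.3 as it is.

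The cost is one sentence in the protocol. Compared with the literal rule there may be a few more screen failures, such as subjects with an isolated raised bilirubin or ALP. Sites that already read the limits as alternatives would see no change.

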4.2.3 Discontinuation of Subjects from Treatment

Subjects should discontinue study treatment for any of the following reasons:

- Withdrawal of informed consent (subject's decision to withdraw for any reason)
- Any clinical AE, laboratory abnormality or intercurrent illness which, in the opinion of the Investigator, indicates that continued participation in the study is not in the best interest of the subject
- If ALT ≥ 5 x ULN on any two consecutive occasions
- Total bilirubin ≥ 2.0 x ULN on any two consecutive occasions
- Pregnancy
- Termination of the study by BMS

UNIT 5 : Treatments

5.1 Investigational Product

An investigational product, also known as investigational medicinal product in some regions, is defined as follows:

A pharmaceutical form of an active substance or placebo being tested or used as a reference in a clinical study, including products already with a marketed authorization but used or assembled (formulated or packaged) in a way different from the authorized form, or used for an unauthorized indication, or when used to gain further information about the authorized form.

In this protocol, investigational product(s) is/are:

Apixaban 5 mg and 2.5 mg tablets and matching apixaban-placebo tablets
Warfarin 2 mg tablets and matching warfarin-placebo tablets

5.2 Identification

The following investigational products will be provided by Bristol-Myers Squibb, Pharmaceutical Research Institute:

Product	Potency	Appearance
Apixaban (BMS-562247) film coated tablets	5 mg	Reddish brown, plain, oval shaped, shallow biconvex film coated tablet
Apixaban (BMS-562247) film coated tablets	2.5 mg	Reddish brown, plain, oval shaped, shallow biconvex film coated tablet
Placebo for apixaban (BMS-562247) film coated tablets	-	Reddish brown, plain, oval shaped, shallow biconvex film coated tablet
Warfarin Sodium (BMS-565793) tablets	2 mg	Lavender, round, biconvex tablet with one face bisected and the other face plain
Placebo for Warfarin Sodium (BMS-565793) tablets	-	Lavender, round, biconvex tablet with one face bisected and the other face plain

5.3 Randomization

Eligible subjects will be randomized in a 1:1 ratio to either apixaban or warfarin titrated to a target INR range 2.0 to 3.0. Subjects who are on warfarin or another Vitamin K antagonist (VKA) will have their VKA discontinued prior to randomization. Each arm will contain ~7.843 subjects. The randomization will be stratified by investigative site and prior warfarin/VKA status (experienced, naïve). Subjects will be classified as warfarin naïve if they have not previously received warfarin or another VKA or have received ≤ 30 consecutive days of treatment with warfarin or another VKA in the past. Otherwise the subject will be classified as warfarin experienced.

Randomization will be stratified according to whether patients had received warfarin previously and according to clinical site. Apixaban or matching placebo will be administered twice daily, with apixaban given in 5-mg doses or 2.5-mg doses will be used in a subset of patients with two or more of the following criteria (5.4.1) : an age of at least 80 years, a body weight of no more than 60 kg, or a serum creatinine level of 1.5 mg per deciliter or more. Warfarin (or matching placebo) will be provided as 2-mg tablets and will be adjusted to achieve a target international normalized ratio (INR) of 2.0 to 3.0. Patients who were receiving a vitamin K antagonist before randomization will be instructed to discontinue the drug 3 days before randomization, and the study drug will be initiated when the INR was less than 2.0. INRs will be monitored with the use of a blinded, encrypted, point-of-care INR device. An algorithm was provided to guide the adjustment of the warfarin dose. The time that patients' INRs will be within the therapeutic range will be

[name]

15

calculated by the Rosendaal method. These data will be reported back to the participating centers with advice for optimal INR control.

At the time of enrollment, each subject will be assigned a unique sequential subject number by the IVRS-Interactive Voice Response System. The IVRS will be available 24 hours per day, seven days a week. The subject number will consist of a unique 5 digit number which is assigned sequentially within a study (starting with 00001) by the IVRS. This number will be used for identification throughout the study and will not be used for any other subject. Each subject who meets the inclusion/exclusion criteria will be randomly assigned to one of two treatment groups: apixaban or warfarin adjusted to a target INR (range 2.0 - 3.0).

5.4 Selection and Timing of Dose for Each Subject

Subjects who are on warfarin or another VKA prior to randomization will have their VKA discontinued or the dose reduced prior to randomization and will not be dosed with study drugs until the INR is < 2.0 . Subjects will receive either apixaban (and warfarin-placebo) or warfarin (and apixaban-placebo) following randomization during a titration phase. Warfarin initiation will avoid loading doses and will be based on several clinical factors. In subjects who are warfarin experienced with adequate INR control, resumption of their previous dosing will generally be the best option.

In subjects who are either warfarin naïve or whose previous dosing history or INR control is not available, age may be the most useful criterion to determine warfarin starting dose. In subjects < 80 years of age, initiation with a daily dose of up to 6 mg of warfarin followed by INR testing on Day 3 or 4 is recommended. In subjects ≥ 80 years of age, initiation with a daily dose of up to 4 mg of warfarin followed by INR testing on Day 3 or 4 should be considered. Subsequent warfarin doses will be recommended based upon an algorithm, the final decision on dosing will rest with the Investigator. INR monitoring will begin on the third or fourth day following initiation of study drug administration and will be performed twice a week for two weeks, once a week for two weeks, and monthly thereafter once a stable INR is attained. An Investigator may increase the frequency of INR monitoring if it is considered clinically indicated.

